### ANALYSIS

The sample size is based on the admissions during 2002-03 and 2003-04 (September 1 – April 30) for elderly ( $\geq$ 65 years old) patients with acute cardio-pulmonary conditions, excluding angina and myocardial infarction. There were 2762 acute cardio-pulmonary admissions during September 1 – April 30 2002-03, and 2852 during 2003-04, i.e., an average of 11.57 admissions ( $\geq$ 65 years) per day.

The study will run for at 666 days (242 during each of Years 1 and 2, and 183 during Year 3), i.e., the number of eligible patients is estimated at 666x11.57=7705.6. We plan to recruit 5 days per week, which reduces the eligible number of patients to  $(5\div7)x7705.6=5504$ . We understand that two-thirds are admitted during the period 09:00-21:00h, which reduces the evaluable pool to 3669. We estimate that three-quarters of eligible subjects will participate, i.e., we expect to recruit 2752 elderly ( $\geq 65$  years old) patients with acute cardio-pulmonary conditions. Of these, 664 are expected to have ICD codes for pneumonia; 556 are expected to have exacerbations of chronic obstructive pulmonary disease; and 735 are expected to be admitted with heart failure.

We estimated the number of admissions in 'high-risk' 18-64 year-olds by extrapolation using (i) national cardio-pulmonary hospital admission data for patients aged 15-59 years, 60-74 years, and 75 years and older and (ii) the number of cardio-pulmonary admissions aged  $\geq$ 65 years in Leicester.

	We assumed that half of the patients admitted with pneumonia, unspecified lower respiratory tract infections, and exacerbations of COPD have underlying high-risk conditions. We expect to recruit 83 18-64-year old patients with pneumonia, 93 with unspecified lower respiratory tract infections, and 181 with COPD. These have not been included in the following estimates: On the basis of historical data we expect that one-third of elderly patients with pneumonia have pneumococcal disease (i.e., 221) but expect the
	number identified by the pneumococcal antigen test to be higher. Of the 221, ~73 should be randomly allocated to the rapid near patient test (Binax NOW) (Group 1); the remainder will be randomised to the group tested by traditional methods (Groups 2 & 3). However, as identical sample sets will be taken from each individual, diagnostic accuracy will be assessed in a minimum of 221 subjects.

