#### 4. URINE

A freshly voided urine sample will be collected from all study participants into standard containers for:

- GROUP 1 ONLY: Near patient testing for pneumococcal antigen using the Binax NOW test by the Study Nurse on the MAU/Ward.
- GROUP 2 ONLY: Prompt testing in the laboratory for pneumococcal antigen using the Binax NOW test on fresh 20 ml concentrated urine.
- GROUP 3 ONLY: Deferred testing for pneumococcal antigen using the Binax NOW test on stored 20ml concentrated urine.
- **GROUP 1 ONLY**: Patients randomised to Group 1 will have near patient tests for pneumococcal antigen done by the study nurse in an area of the MAU/ward where urinalysis is done routinely. A description of the test kit and obstructions for doing the test is provided in Appendix X. On completion of the test the Study Nurse will:
  - (a) Record the test result in the CRF;
  - (b) Inform the team (i.e., the responsible nurse and/or doctor) that is providing clinical care of the patient of the rapid near patient test result (i) verbally; and (ii) by insertion of an adhesive label in the notes. The clinical team should be told that a negative test does not exclude infection with with *S. pneumoniae*.
  - (c) Document in the CRF the time that the team was informed, and who was told.

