#### 6.2 Follow-up (Days 2, 3, 4,5,6 7,8,9,10, and 28)

#### 6.2.1 Time when diagnostic results were made available (Days 2, 3, 4, 7, and 10)

The times when the relevant diagnostic test results (See below) were made available to the medical and nursing team providing clinical care will be recorded in the CRF by reference to the APEX Pathology Computerised records system, and/or records held by the Department of Microbiology and Molecular Diagnostic Laboratory. Thus the times that the following test results were available will be entered into the CRF, even if the patient is discharged or has died:

Group 1:	
Rapid tests:	Rapid near patient test for influenza A and B (Quidel QuickVue influenza A and B)
	Near patient pneumococcal antigen test (Binax NOW test)
Conventional tests:	Viral culture test results (influenza A and B, RSV)
	Sputum Gram stain result
	Sputum culture result
	Blood culture result
Group 2:	
Rapid tests:	Rapid molecular tests for influenza A and B and RSV A and B,
	Laboratory pneumococcal antigen test (Binax NOW test) using concentrated urine
Conventional tests:	Viral culture test results (influenza A and B, RSV)
	Sputum Gram stain result
	Sputum culture result
	Blood culture result
Group 3:	
Conventional tests:	Viral culture test results (influenza A and B, RSV)
	Sputum Gram stain result
	Sputum culture result
	Blood culture result

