- Based on the above, we expect to recruit 747 participants with pneumonia, of whom at least one third (n=249) should have *S. pneumoniae* infection. Of these, ~83 should be randomly allocated to the rapid near patient test (Binax NOW); the remainder will be randomised to the group tested by traditional methods. Thus the speed of diagnosis, impact of early diagnosis on prescribing, clinical outcomes, and costs will be assessed in groups having an estimated 83 and 166 subjects. However, as identical sample sets will be taken from each participant, the diagnostic accuracy of the tests will be assessed in all 249 subjects. The number of cases of *S. pneumonaie* infection that are likely to be identified among the anticipated 649 (556 +93) participants with unspecified acute lower respiratory tract infections is unknown, but their occurrence will add to the pool of cases for studies of diagnostic accuracy.
- On the basis of the Rochester study, we expect that 10% of the 2752 elderly (≥65 years) participants will have influenza A or B. Of the 275, one third (~92) will be allocated to the QuickView near patient influenza immunoassay; one third will be allocated to the rapid molecular group; the remainder will be allocated to the group tested by traditional methods. Identical sample sets will be taken from each individual, so the diagnostic accuracy of the tests will be assessed in all 275 subjects.
- Similarly, we expect that 5% of the 2752 elderly (≥65 years) participants will have RSV A or B. Of the 138, one third (~46) will be allocated to the rapid molecular group; the remainder (~92) will be allocated to the group tested by traditional methods. We expect that very few of these will be found

positive by the routine tests employed. Identical sample sets will be taken from each individual, so the diagnostic accuracy of the tests will be assessed in all 138 subjects.

While the numbers of patients with influenza and RSV who are allocated to the 'rapid' near patient or molecular tests are comparatively small (~92 + ~46 per elderly group, plus cases occurring in the 18-64-year-olds), the impact of a 'viral' infection (RSV or influenza) infection on patient isolation, antimicrobial prescribing, and clinical outcomes may be compared using a larger combined group – i.e.,

Elderly

Rapid influenza & RSV (i.e., Quickview + molecular tests) n=(92+92+46)=230Traditional influenza & RSV n=(92+46+46)=184

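### For S. pneumoniae the sample-size text counts Group 2 as traditionally tested, although Group 2 receives a prompt antigen result and the endpoint section sets Groups 1 and 2 against Group 3.

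*Protocol*

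**What the plan says.** Two places treat Group 2 as a control group for pneumococcus.

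- Synopsis, Sample size: it expects that "one-third of elderly patients with pneumonia have pneumococcal disease (i.e., 221"). It continues "Of the 221, ~73 should be randomly allocated to the rapid near patient test (Binax NOW) (Group 1"), and "the remainder will be randomised to the group tested by traditional methods (Groups 2 & 3").
- Section 7.1: "we expect to recruit 747 participants with pneumonia, of whom at least one third (n=249) should have" pneumococcal infection. About 83 go to the near patient test and the rest to the traditional group. Speed of diagnosis and the "impact of early diagnosis on prescribing, clinical outcomes, and costs will be assessed in groups having an estimated 83 and 166 subjects".

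Elsewhere Group 2 is a rapid-test group for the same organism.

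- Sections 4.1 and 6.1.13 define Group 2 as molecular viral tests plus laboratory pneumococcal antigen testing. Section 4.1 adds that Groups 1 and 2 are given the rapid results of their own group.
- Section 6.1.14, item 4 (Urine), specifies for Group 2 "Prompt testing in the laboratory for pneumococcal antigen using the Binax NOW test on fresh 20 ml concentrated urine". For Group 3 the same assay is deferred and run on stored urine.
- Section 6.2.1 lists "Laboratory pneumococcal antigen test (Binax NOW test) using concentrated urine" among the rapid tests of Group 2 whose availability to the clinical team is timed. Group 3 has conventional tests only.
- Section 6.2.8 selects antigen-positive patients from Groups 1 and 2 for a blood sample within five days of admission, so the Group 2 result must be known early.

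Section 7.5.1 (and the synopsis endpoints) compares S. pneumoniae patients in Groups 1 and 2 with Group 3 for fever, oxygen and CPAP dependence, and quality of life. It reports the other S. pneumoniae outcomes by Groups 1, 2 and 3. Section 7.6 describes three-group comparisons.

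**The concern.** A patient in Group 2 with pneumococcal infection may have a positive antigen result on the ward early in the admission, which is the exposure under study. Placing that patient with the controls makes half of the comparator a rapid-test group. Any effect of a rapid result on prescribing, outcome or cost would then be measured against a group that has partly received it, and the contrast would shrink towards no difference.

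The error is specific to pneumococcus. The synopsis also places Group 1 with Group 3 as traditional for RSV, but that is correct, because Group 1 has no rapid RSV test.

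This is more than a loose label, because Section 7.1 states that the impact measures will be assessed in groups of these sizes. An analyst who follows that sentence and one who follows Section 7.5.1 would run different comparisons on the same patients.

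**Working it through.** **Reproducing the plan's counts**

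- Elderly: 664 pneumonia cases / 3 = 221.3. One third of these is 73.8 and the remainder is 147.6. The synopsis gives 221 and about 73, leaving 221 − 73 = 148.
- All ages: 664 + 83 = 747 pneumonia cases; 747 / 3 = 249; 249 / 3 = 83; 249 − 83 = 166. Section 7.1 gives 249, 83 and 166.

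The counts reproduce. The 166 can only be Groups 2 and 3 combined (2 × 83).

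**Dilution**

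Let *d* be the true difference between Group 1 and Group 3, and *f·d* that between Group 2 and Group 3. The documents do not give *f*; I take 0 to 1 as the range. With equal allocation, the pooled Groups 2 and 3 lie *f·d*/2 from Group 3, so Group 1 v Groups 2+3 estimates *d*(1 − *f*/2). Groups 1+2 v Group 3 estimates *d*(1 + *f*)/2.

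**Precision**

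With a common standard deviation, the standard error is proportional to:

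- 83 v 166 (either way round): √(1/83 + 1/166) = 0.1344
- 83 v 83: √(1/83 + 1/83) = 0.1552

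The gain from unequal pooling is 0.1552 / 0.1344 = 1.155. Multiplying by the share of *d* recovered gives the expected z-statistic relative to a clean Group 1 v Group 3 comparison:

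| *f* | Share of *d*, Group 1 v 2+3 | Relative z, Group 1 v 2+3 | Share of *d*, Groups 1+2 v 3 | Relative z, Groups 1+2 v 3 |
|---|---|---|---|---|
| 0 | 100% | 1.155 | 50% | 0.577 |
| 0.5 | 75% | 0.866 | 75% | 0.866 |
| 1 | 50% | 0.577 | 100% | 1.155 |

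Group 1 v Group 3 estimates *d* whatever *f* is, and Group 2 v Group 3 estimates *f·d*. The shares apply to differences in means or proportions; for hazard ratios they are only a guide.

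**Dependence of stated power on the split**

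Section 7.4 gives precision for diagnostic accuracy and power for length of stay and isolation, all from 2752 elderly patients. None of these uses 83 v 166 or 73 v 148, so none changes.

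**The case against.** The strongest reply is that the endpoint and analysis sections already have the right structure. Section 7.5.1 never pools Group 2 with Group 3, Section 7.6 analyses three groups, and the synopsis assessment methods set Groups 1 and 2 against traditional culture in Group 3. On this view the misplaced label sits only in text about expected numbers. Much of this stands: the bias arises only where the Sample size and Section 7.1 grouping is followed. It does not remove the contradiction, because Section 7.1 says what will be assessed and in which numbers.

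Four stronger readings are tempting but not supported.

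- *Every pneumococcal contrast is biased.* The endpoint text does not use the split.
- *The effect is halved.* That is the upper bound and needs *f* = 1. The routes differ: a bedside test reported verbally by the study nurse in Group 1, and urine sent to the laboratory in Group 2.
- *Power falls from 80% to 37%.* A relative z of 0.577 does imply this (2.80 × 0.577 − 1.96 = −0.34, or 37%), and 0.866 implies 68%. But the 80% is a hypothetical start for an 83 v 83 comparison; the protocol claims no power for it.
- *Harm from early streamlining of antibiotics would be hidden.* Section 10.4 relies on notification of each death with study group, on case review, and on rapid against conventional diagnosis. It does not refer to 83 v 166, and Section 7.6 compares mortality across three groups.

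**Conclusion.** The concern holds as an internal contradiction over the pneumococcal comparator. Group 2 is a rapid-test group for S. pneumoniae under Sections 4.1, 6.1.14 and 6.2.1. The synopsis Sample size text and Section 7.1 are wrong to count it as traditional, and the stated 83 v 166 (elderly about 73 v 148) follows from that mistake. If this split were analysed, the Group 1 effect would be diluted by 0 to 50%: 25% at half effect and 50% at equal effect. The range rests on equal allocation and on an unknown *f* between 0 and 1. No stated power figure is affected, and the endpoint section, if followed, avoids the problem.

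**What to change.** - In the synopsis, Sample size, delete the statement that Groups 2 and 3 are the traditionally tested group for pneumococcus.
- In Section 7.1, delete the matching sentence on the remainder and the group sizes 83 and 166.
- In both places, state that Group 3 is the only traditional comparator for S. pneumoniae. The main contrasts are Group 1 v Group 3 and Group 2 v Group 3, with about 83 patients per group (about 74 in the elderly), in line with Section 7.5.1.
- A pooled comparison of Groups 1+2 with Group 3 (166 v 83) may be added as secondary. Note beside it that it gains precision only if the two rapid routes have similar effects: relative z is 1.155 at *f* = 1, but 0.866 at *f* = 0.5, no better than the split being replaced.

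The cost is a wording change, with nothing altered in recruitment, randomisation or testing. The downside is that each pairwise contrast has 83 rather than 166 controls: its standard error factor is 0.1552 instead of 0.1344, about 15% larger.

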#### Quality of Life (EQ-5D)

Quality of life in the three diagnostic groups will initially be compared using non-parametric methods. Further analyses to allow for potential differences in patient demographics and baseline clinical characteristics between the three diagnostic test groups, and not allowed by stratification, will make use of generalised linear models in order to accommodate any skewness in the data.

#### Speed of Tests

Time taken to receive test results in the three diagnostic groups will initially be compared using non-parametric methods. Further analyses to allow for potential differences in patient demographics and baseline clinical characteristics between the three diagnostic test groups, and not allowed by stratification, will make use of generalised linear models in order to accommodate any skewness in the data.

#### Cost Data

Cost data will be analysed using parametric and non-parametric statistical methods which explicitly allow for the censoring of (indirect & total) costs at 28 days, i.e. for those patients who are not discharged from hospital within 28 days and thus enable an unbiased assessment of potential cost differences between the three diagnostic groups to be made. Estimation of the cost distribution over longer timescales will make use of extrapolation techniques using time of discharge obtained from hospital information systems.

	Study Day			
	Admission	Days	Day 28	
Assessments	(Day 1)	2, 3, 4, 7 ( + 1), & 10 ( + 1)	( + 2)	
Pre-study assessment by admitting medical team	✓			
Note time of admission (CRF)	$\checkmark$			
Inclusion/Exclusion criteria check (CRF)	~			
Written informed Consent (or Assent) (CRF)	~	✓ (Consent upon recovery)		
Demography/immunisation status check (CRF)	~			
Medical history/concomitant medications check (CRF)	~			
Symptom assessment (CRF)	~			
Clinical findings, including body weight and temperature (CRF). Establish when patient first becomes apyrexial ( $\leq$ 37.2°C), requires supplemental O 2 , and remains so for >24 hours (CRF)	1	✓ (temperature, O 2 )		
EuroQol. Quality of Life assessment (CRF)				
MRC Dyspnoea Scale	~			
Physical Activity Questionnaire		✓		
Diagnostic studies ordered by the admitting medical team (CRF)	~	$\checkmark$		
Collection of trial specific diagnostic specimens (CRF):	~	✓ (antibody, Day 10- 90)		
Nasopharyngeal (Quidel & virus culture) Nasopharyngeal Swabs Sputum (Gram stain & culture) Urine (Binax NOW) Blood (Blood cultures, serum antibodies)		Day 2-3 if first swabs positive if available.		
Record time when diagnostic test results were made available to the ward nurses, and/or admitting team (CRF)	~	4		
Record antimicrobials & antivirals (identity,route, dose, time of administration) prescribed by admitting medical team (CRF)	~			
Note the time of any changes in antimicrobials & antivirals (identity,route, dose, time of administration) prescribed by admitting medical team (CRF)		1		
Bed location, i.e., record bay or a single room (CRF)	~			
Note time of any subsequent change in isolation status (CRF)		$\checkmark$		
ITU and ventilatory support: Document whether admitted or required ventilatory support (CRF)	~	¥		
Date of hospital discharge/ Death within 28 days of admission (CRF)		✓		
Discharge diagnosis (CRF)		✓		

## TRIAL PLAN AND SCHEDULE OF ASSESSMENT

Note: Patients WILL NOT be re-recruited if readmission occurs during the 28-day follow-up

#### 1 BACKGROUND AND RATIONALE

#### 1.1 Elderly demographics

Western industrialized nations face a population explosion among the elderly. In the UK the population aged  $\geq$ 65 years, currently at ~12%, is projected to exceed the 1-14 years group by 2025 and surpass 20% overall by 2025. The number of people of state pension age is projected to increase by 10.2% between 2000 and 2011. Preparation for this population growth, including the prevention and care of their illnesses is of paramount importance.

#### 1.2 Acute respiratory illnesses

Illness surveys conducted in general practice indicate an overwhelming importance of acute respiratory illness in comparison to other conditions. During the most recent National Morbidity Study, a higher proportion of people (31%) consulted for respiratory conditions at least once during the year than for diseases in any other single ICD chapter. Overall, 67% of patients who saw their GP with a respiratory condition did so because of an acute infection, i.e., ~20% of all consultations in primary care occur because of acute respiratory infections, which are mostly viral. A similar picture has emerged in the United States. Some important age differences have emerged. There is a very high incidence of 'colds' and lower respiratory illness in the very young, whereas in the elderly, there is an age-related increase in morbidity and mortality from 'pneumonia and influenza.' We propose in this study to evaluate rapid diagnostic technologies for three target pathogens, influenza, respiratory syncytial virus, and *S. pneumoniae*, which are key aetiological agents of acute respiratory illness, and collectively are responsible for considerable morbidity and mortality in the elderly.

There have been no studies of the comparative incidence of influenza, RSV and pneumococcal disease among elderly cardiopulmonary admissions. Falsey *et al* evaluated the number of hospitalisations of RSV infection relative to influenza in several thousand elderly people admitted to six hospitals in New York State between November and April 1989-1992. This and other studies suggest that RSV is likely to be found in ~5% of patients hospitalised with acute respiratory disease, though with molecular diagnostic tests, the number identified is likely to be higher. Previous studies indicate that at least 10% of cardiopulmonary admissions have influenza, but the number of admissions is influenced by the severity of epidemics, which have been mild since 1999/2000. None of these studies were conducted in the United Kingdom, and referral and admission practices may differ between countries. About one-third of all patients who are hospitalised in Northern Europe with community-acquired pneumonia have *S. pneumoniae* infection.

#### 1.3 Influenza

About 20% of children and 5% of adults worldwide develop symptomatic influenza A or B each year. Although influenza A and B viruses circulate virtually every winter, quantification of the burden of influenza on consultations, emergency department examinations, hospital admissions, and mortality has been difficult because influenza lacks pathognomonic features, it co-circulates with other respiratory pathogens, and it causes a range of non-specific complications, such as exacerbations of chronic cardiopulmonary disease. During outbreaks, sentinel schemes, such as the Royal College of General Practitioners network in England, report increased consultation rates for influenza-like illness (ILI) and other respiratory syndromes that are

strongly associated with excess mortality. In England and Wales, an estimated 6,200 to 29,600 people died during each of the epidemics between 1975-76 and 1989-90. These estimates are about ten times the number of death certifications for influenza, because the disease is the cause of many 'hidden deaths'. About 90% of these influenza-associated excess deaths are among people aged 65 years and older. Although there are age-related increases in deaths from influenzal illness in both 'at-risk' and 'low-risk' groups, most deaths and hospitalisations occur in elderly people with chronic cardiopulmonary disorders. The burden of influenza on winter admissions is poorly reflected by hospital activity analysis – as shown by our recent study of rapid molecular diagnosis of paediatric admissions in Leicester. We found that very few children with influenza were diagnosed or coded correctly. Moreover, analysis of hospital activity statistics for Leicester for winters 2002/3 and 2003/4 revealed that only 2 of 5614 cardiopulmonary admissions among the elderly had a laboratory-confirmed diagnosis of influenza. We believe that this grossly underestimates the true burden of influenza in hospitals and reflects the views of hospital doctors that conventional diagnostic virology for respiratory pathogens is of no clinical value.

#### **1.4 Respiratory syncytial virus**

Respiratory syncytial virus (RSV) is a negative strand RNA virus belonging to the *Pneumovirus* genus of the *Paramyxoviridae* family. Respiratory syncytial virus (RSV) has a global distribution, causing sizeable outbreaks annually, usually between November – May. There are two antigenically distinct subtypes of RSV designated A and B; strain differences exist within each subgroup. Natural RSV infection produces incomplete protection and reinfection with RSV is common. Like influenza, RSV infection in the elderly has no pathognomonic features, and its distinction from other respiratory virus infections is impossible clinically. Evidence is accumulating that RSV is an important pathogen for the elderly, causing illness that is indistinguishable from influenza with upper respiratory symptoms that are frequently associated with lower respiratory tract involvement and pneumonia. Outbreaks in residential care facilities are well documented and are of particular concern due to their high morbidity and mortality. Pneumonia occurs in 5% to 55% of cases, and mortality rates of up to 20% have been described. Because RSV has traditionally been considered a paediatric infection, evidence of the virus in community-dwelling elderly, or admissions with cardiopulmonary disorders is usually not sought.

The lability of RSV; its brief period of shedding and low titre in nasal specimens during reinfection; the relative insensitivity of the complement fixation test (CFT), cell culture (even when performed under rigorous conditions including bedside inoculation) and rapid antigen detection tests (immunofluorescence and Directigen enzyme immunoassay) in the elderly; and the frequent co-circulation of RSV with influenza, may contribute to an underestimation of its incidence and burden.

Data from a prospective population-based study of upper respiratory tract infections in community dwelling elderly in Leicester, England demonstrated 3.6 RSV infections per 100 person years. Eighty-two percent (9 of 11) in the RSV subgroup had lower respiratory illness, 45% (5/11) were seen by a medical practitioner, and 36% (4/11) received antibiotics. A study of subjects with underlying chronic lung disease or congestive heart failure in Rochester, NY, reported an incidence of 4.3 RSV infections per 100 person winters. The clinical impact of RSV was considered significant as three of the eight RSV-infected subjects were

hospitalised. A more recent study by these investigators identified a rate of 3.7 RSV infections per 100 person winters in a healthy elderly population. Two of 12 RSV-infected elderly had complicated RSV illnesses (1 pneumonia on X-ray, 1 hospitalised), 5 (42%) required physician visits, and 4 (33%) received antibiotics.

